be considered an adverse event in the setting of normal subject values prior to taurine supplementation. Any intercurrent illness or injury that represents an exacerbation of pre-existing condition (e.g., increase frequency or severity) will also be considered an AE. In such cases it will be preferred to record the diagnosis as the AE rather than a series of terms relating to the diagnosis (e.g., worsening of asthma). An adverse drug reaction will be all noxious and unintended responses to taurine product. This means that a causal relationship between taurine and an AE is at least a reasonable possibility (i.e., the relationship cannot be ruled out).

The PI and one of the co-investigating MDs will determine the severity of the event and if the SAE or AE is related to the protocol using the categories noted below. Review of their determination will be sought from the Safety Officers. In the case of deferring opinions, higher grade of severity the more related rating will be accepted

Grade	Description
Mild	No limitation of usual activities
Moderate	Some limitation of usual activities
Severe	Inability to carry out activities

Not Related	The adverse finding was present prior to exposure to the investigational product, having the same or milder intensity OR The finding is considered likely to be related to an etiology other than the investigational product, that is, there is no evidence or arguments to suggest a causal relationship to the investigational product.
Possibly related	Exposure to investigational product and onset of the finding are reasonably related in time AND The adverse finding could be reasonably be explained by factors or causes other than exposure to investigational product.
Probably related	Exposure to investigational product and onset of the finding are reasonably related in time AND The adverse finding is more likely explained by exposure to investigational product than by other factors or causes.

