SAEs will be reported to one of the co-investigator MDs as well as the Safety Officers, FDA, COMIRB, the CTRC within five working days of knowledge of the event. The participant's PCP will also be notified if deemed appropriate by the co-investigator MD. Unanticipated problems or events that result in an actual unforeseen harmful or unfavorable occurrence to the subject or others with also be reported to one of the co-investigating MDs within five working days of knowledge of the event. Information that indicates a change to the risks or benefits of the study will also be reported within five days of discovery to the Safety Officers,

FDA, COMIRB and CTRC. No new patients will be enrolled or studied until the SAE has been reviewed and appropriate action taken by the above listed bodies.

The PI will notify co-investigator MDs of abnormal safety monitoring lab results within five working days of resulted values. If deemed clinically appropriate by co-investigator MD, the subjects PCP will be notified. All other AEs will be logged and reported to COMIRB yearly or at the time of continuing review.

For full list of events to be reported to COMIRB see the Reportable Event Sheet to be used for monitoring and tracking individual events attached in Appendix V - Supplemental Materials.

A summary of data monitoring and reporting flow during the active portion of the study is noted below. A flow diagram of this information can be found in Appendix V - Supplemental Materials in the CTRC protocol application.

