	emotional mood			
	Other			
Allergic/Immunologic				
	reactions to drugs/foods			
	Other			

III. Reportable event sheet

Oxidative Stress Markers in Inherited Homocystinuria and the Impact of Taurine
Reportable Event Sheet

	EVENT	Date of Knowledge of Event	Date Reported to COMIRB	Comments
	Unforeseen harmful/unfavorable event, felt to possibly be related to study			
	injury			
	psychological event			
	other			

Unforeseen harmful/unfavorable event, felt to be unrelated to study			
injury			
psychological event			
other			
Unforeseen development that increases likelihood of harm			
midterm review			
new safety data on taurine supplementation			
other			
Problem involving data			
data collection			
data storage			
data privacy			
data confidentiality			
Change in subjects status			
incarceration of subject			
pregnancy of subject			
other			
Change in protocol for subject safety done prior to COMIRB review			
apparent immediate hazard			
Complaint of participant that can't be resolved or suggest risk			
complaint			
Unintentional protocol violation that harmed or may cause harm			
violation			
Noncompliance by the PI or research team			
noncompliant activity			
Other			
other			

IV. Advertisement for subject recruitment

Advertisement for subject recruitment:

You are invited to participate in a study investigating homocystinuria. The study is being conducted by (Site Specific Providers) at (Site Location). The study investigates why individuals with homocystinuria have health problems and if a new investigative treatment with taurine is beneficial. The study will not provide direct benefit to the participant but will provide generalizable information on homocystinuria.

To be eligible to participate in the study individuals must be between the ages of 8 to 50 year and have a diagnosis of homocystinuria due to cystathionine beta-synthase deficiency that is not fully responsive to therapy with total homocysteine (tHcy) levels greater than 50 $\mu\text{mol/L}$. Individuals cannot participate if they are (1) pregnant, (2) have hypertriglyceridemia, (3) have another significant illness, and/or (4) are being treated with Vitamin C, taurine supplementation, and/or high dose antioxidant supplementation and cannot discontinue this.. Participants who have a cold, the flu or other short term illness will be asked to delay participation until they are recovered.

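### The Section 8.B relatedness table is defined only against taurine, so an SAE caused by a study procedure before the first dose is rated *Not Related* and does not reach the Section 8.C stopping criterion through the table

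*Combined protocol and SAP*

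**What the plan says.** Section 8.B gives the relatedness decision to the PI and a co-investigating physician, with review by the Safety Officers. The task is to determine "if the SAE or AE is related to the protocol using the categories noted below". Three categories follow:

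- *Not Related* has two alternative limbs. The second is met when "The finding is considered likely to be related to an etiology other than the investigational product", explained as no evidence or argument for a causal link to the product.
- *Possibly related* and *Probably related* share one entry condition: "Exposure to investigational product and onset of the finding are reasonably related in time". They differ in whether other causes could reasonably explain the finding or the product is the likelier explanation.

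Section 8.C uses relatedness to the protocol, not to taurine. One SAE at least possibly due to the protocol is both a ground for discontinuing the subject and a ground for suspending the study pending review.

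On timing, Section 5.G places the baseline studies before taurine. Section 8.B puts Day 1 one day before taurine. The Section 5.H schedule puts endothelial function studies on Day 1 and again on Day 6. Section 5.G includes 0.4 mg sublingual nitroglycerin in that session for adults.

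**The concern.** The raters are asked about the protocol, but the categories answer only about the product. Where the two diverge, the rating can be wrong on the question asked. They diverge most clearly before the first dose, when the subject has undergone study procedures but has had no taurine.

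At stake is the one Section 8.C rule meant to act on a single serious event. If it is not triggered, a subject harmed by a study procedure is not formally discontinued and stays scheduled for taurine dosing and the repeat Day 6 session. Others already in the schedule are not covered by a formal suspension.

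**Working it through.** The plan states no figure on this point, so the check is to apply the table as written to test cases and follow the rating into Section 8.C.

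**What the categories refer to.** Mentions of the investigational product: *Not Related* 3 + *Possibly related* 2 + *Probably related* 2 = 7, in 3 of 3 categories. Mentions of a procedure, the study or the protocol in the same cells: 0. The product is taken to be taurine because the paragraph above the table defines an adverse drug reaction in terms of taurine. Nitroglycerin is never called investigational.

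**Test case A: an adult is hospitalised for hypotension after nitroglycerin on Day 1.**

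1. *Probably related* needs prior exposure to taurine. There has been none, so it fails.
2. *Possibly related* has the same entry condition, so it fails.
3. *Not Related*, second limb: the likely cause is something other than taurine, so it is met.

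The only available rating is *Not Related*, although the event came from a protocol procedure. A serious complication of venous access before dosing gives the same result.

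**Test case B: the same event after the Day 6 session.** Taurine exposure has occurred, onset can be reasonably related in time, and another cause could explain the finding. *Possibly related* is available. The clear gap is therefore confined to the period before the first dose.

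**Following case A into Section 8.C.**

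| Criterion | Met by case A through the table? |
|---|---|
| Suspension: one SAE at least possibly due to the protocol | No, rated *Not Related* |
| Suspension: liver, triglyceride or hypotension thresholds | No, needs two or more subjects with normal values before taurine |
| Suspension: clinically significant safety laboratory change | No, same two-subject and pre-taurine conditions |
| Discontinuation: SAE at least possibly due to the protocol | No, rated *Not Related* |
| Discontinuation: positive pregnancy test | Not applicable |

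**What happens regardless of the rating.** Every SAE is discussed with a co-investigating physician within 24 hours (Section 8.A). It is reported to the FDA, COMIRB, the CTRC and the Safety Officers in five working days (Section 8.B). It leads to a meeting of the Safety Officers and investigators within a week of the report (Sections 8.A and 8.B). New patients are held until the review bodies have acted (Section 8.B). What depends on the rating is formal discontinuation of the subject and formal suspension for anyone already in the six-day schedule.

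**The case against.** The best defence is that the result depends on a very literal reading. Raters are asked about the protocol, and Section 8.C asks about the protocol again. A physician who has just admitted a subject after study nitroglycerin would hardly say the event had nothing to do with the protocol. Safety Officers independent of the study review the rating, and where opinions differ the more related rating prevails. The exposure is also limited: one 0.4 mg dose, adults only, withheld below 105 mmHg systolic and in users of PDE5 inhibitors, with uncontrolled hypertension and recent cardiovascular events excluded. By the plan's own SAE definition the affected subject has died or been hospitalised, so physicians would be making decisions anyway.

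Much of this stands, and it limits the consequence. It does not remove the defect. Section 8.B tells the raters to use these categories. The tie-break works only if someone disagrees, and it supplies no procedure category. Nothing says that the wording of Section 8.C overrides the table.

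Three stronger readings are tempting, and the documents do not support them.

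- *The table also conflicts with Section 8.A and the Reportable Event Sheet.* Section 8.A lists what to look for and attaches no rating rule. The sheet, described as the "Reportable Event Sheet to be used for monitoring and tracking individual events", has a row for "Unforeseen harmful/unfavorable event, felt to possibly be related to study" and a parallel row for events felt to be unrelated. Both have a column for the date reported, so a differing label does not lose the report. Only Section 8.C ties an action to the rating.
- *The first limb of* Not Related *dismisses a pre-existing finding that worsens on taurine.* That limb reads "The adverse finding was present prior to exposure to the investigational product, having the same or milder intensity" and names no clear comparator. But the same section says an "exacerbation of pre-existing condition (e.g., increase frequency or severity) will also be considered an AE", and defines an adverse drug reaction as one where "a causal relationship between taurine and an AE is at least a reasonable possibility (i.e., the relationship cannot be ruled out". Those sentences point the other way, so this is at most ambiguous drafting.
- *Such an SAE would escape review.* It would not, because the reporting and review steps do not use the rating.

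**Conclusion.** The point holds as a minor defect. It is a stated rule that misclassifies a definable kind of event: as written, an SAE caused by a procedure before dosing is *Not Related*, and the Section 8.C criterion is not met through the table.

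This rests on two assumptions: that the investigational product means taurine, which is clear from context though not defined in the table, and that raters follow the table rather than answering the Section 8.C question directly. A rater who did the latter would reach the right result.

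The size cannot be put as a rate. The documents give no SAE frequency and no accrual rate from which to judge how many subjects overlap in the schedule. Up to 20 may consent and up to 16 be exposed to taurine, and Section 8.A says an SAE is not anticipated. Few events, possibly none, would be affected.

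**What to change.** Keep the existing table as the rating of relatedness to taurine. Add a parallel *Not*, *Possibly* or *Probably related* rating for study procedures, naming the endothelial function session with nitroglycerin, venous access and blood draws. State in Section 8.C that its SAE criterion is met if either rating is at least *Possibly related*.

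Two ratings are better than adding procedures to the existing wording. With draws and other procedures throughout the six days, almost any event would follow some procedure in time, so nearly every SAE could qualify as possibly related and suspend the study. A merged rating would also blur taurine causality, which this pilot needs to keep separate.

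The cost is one extra rating per event and possibly a few more events counted as related. No visit, sample or analysis changes.

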- 11-dehydro-thromboxane B2 (11-dehydro-TXB2) and 2,3-dinor-TXB2, urine

Bone mineral density by DEXA

B. Secondary Outcome Measure(s):

The relationship between the above noted oxidative stress markers and the related methionine cycle metabolites will be assessed

- Hcy
- Methionine
- Cystathionine
- Cysteine
- SAM (S-adenosylmethionine)
- SAH (S-adenosylhomocysteine)
- Dimethylglycine
- Betaine

Lipoprotein A will be assessed as confounding variable potentially modulating platelet aggregation and inflammatory response.

Molecular studies will be done given the known genotype/phenotype correlations in this disease and for verification of diagnosis.

Pharmacokinetic studies of taurine will be done for the first 12 hours following the first dose of taurine, and a steady state concentration will be obtained after 4 days of treatment.

C. Study Population Description:

Participants will be recruited from the Inherited Metabolic Diseases Clinic at Children's Hospital Colorado, The Children's Hospital of Philadelphia, and Duke University Hospital. Recruitment of patients being followed by other metabolic clinics may also be pursued if additional participants are needed. This will be done through their metabolic physician and / or through family support groups. Patients must meet all inclusion criteria. There will be no discrimination based on age, gender, or ethnic heritage.

D. Total Planned Number of Subjects:

- a. **For Single-Center Studies:** NA
- b. **For Multi-Center Studies – Up to 20**
 - i. **For this location: Up to 12**
 - ii. **For all locations: Up to 20**

Up to 16 patients will be exposed to taurine and analyzed. Allowing for 20 patients to sign consent is based upon the potential for patients who withdraw consent prior to drug exposure, may be potential screen failures, or fail to proceed to study after signing consent.

E. Inclusion Criteria:

Minimal inclusion criteria are:

1. A confirmed biochemical, molecular, or enzymatic diagnosis of classic homocystinuria due to cystathionine beta-synthase deficiency (OMIM 236200)
2. And not fully responsive to therapy (eg, tHcy levels above 50 $\mu\text{mol/L}$ on therapy including on B6 therapy)
3. Be over 8 years old and less than 50 years. The first four patients will be adults (age 18 – 50 years).
4. Be able and willing to provide informed consent

Exclusion Criteria:

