The study will usually start on a Thursday and end on a Tuesday to allow for the four day treatment period with blood and urine sample collections and ultrasound and FMD studies to be done on work-week days. Laboratory will be taken at 8:00 AM after overnight fasting or at 12 noon before lunch and after a 3 hour fast to limit the impact of dietary intake of protein . Should the taurine study be terminated early, then laboratory studies and FMD studies may be collected earlier at closing. Taurine will be dispensed by the centers investigational pharmacy, enough product given for the total length of the study. Bottles of product will be collected at the end of the study and amount of left-over product determined as a compliance check in addition to participant self-report compliance. Participants will be asked to stop use of any anti-oxidation supplement, in excess of standard multi-vitamins (1 table/day) for two weeks prior to the study. They will also be requested to avoid use of non-prescription salicylates (Aspirin) two weeks prior to the study. Potential confounding variables of (1) hormone replacement therapy, (2) other significant chronic disease (3) high physical activity, (4) smoking habits, and (5) anticoagulant use will be determined for each individual. Safety will be assessed by vital signs and a physical examination, a questionnaire on possible side effects, and basic laboratory tests of CBC, CMP, and lipid panel.

Molecular analysis of the CBSDH gene will be done in the Children's Hospital Colorado DNA Diagnostic laboratory, where this test is clinically available. We anticipate that about half the patients will already have this information clinically available, with about half the patients requiring further analysis as part of this study.

H. Laboratory Assays, Examinations and Procedures:

Study	Purpose	Laboratory
Luminex, 8 plex (IL-1 α , IL-1 β , IL-1ra, IL-4, IL-6, IL-10, TNF- α , MCP-1, IL-8, IL-12p70, IL-17, MIP-1 α , MIP-1 β)	inflammation	CTRC
CRP	inflammations	CTRC
Myeloperoxidase	oxidative stress	CTRC
TGF-beta	inflammation	CTRC
superoxide dismutase	oxidative stress	[name]/UCD
TBARS	oxidative stress	[name]/UCD
Elisa assay (IL-1 α ,IL-1 β , IL-10, TNF- α)	inflammation	[name]/UCD
Isoprostane, urine	oxidative stress	[name]/Duke University
Dityrosine, urine	oxidative stress	[name] Anesthesiology Laboratory
Glutathione, whole blood	oxidative stress	[name]/ Stanfod
tHcy	disease primary marker	Metabolite Laboratory, Inc

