Special Care Clinic
[name]
[name]

[name]
[contact]
[name]

[name] (alternate)
[contact]
[name]

Unanticipated problem or events, especially problems or events that are possibly or probably related to the study or research procedures will also be looked for. This includes monitoring for serious adverse events (SAEs) since such an event is not anticipated. In an event of an SAE, the monitoring PI will discuss the event with one of the co-investigator MDs within 24 hours of knowledge of the event to allow for decisions regarding the data and the safety to all participants. All unanticipated problems and unanticipated events will also be discussed with one of the co-investigating MDs within five working days of knowledge of the problem or event. Any identified trend in AEs will also be discussed within five working days of knowledge of the trend with one of the co-investigator MDs. Of note, the minimal risk for adverse events relative to taurine intake, the low number of participants (N=16 with drug exposure) and short duration of the study (5 days) make it very unlikely that any AE trend would be detected much before the end of the study.

There are no conflicts of interest for the PI or the co-investigator MDs responsible for data safety management.

B. Describe SAEs and AEs for this protocol and the SAE/AE reporting plan:

Events that result in death, immediate hospitalization, or prolonged hospitalization to prevent death or serious disability will be considered SAEs. Any other untoward medical occurrence temporally associated with the study will be considered AE. This includes headaches, gastrointestinal discomfort, and other events captured on the adverse event/compliance sheet that are without significant health risk and/or are potentially unrelated to study. Clinically significant changes in blood pressure or safety monitoring labs will be considered an AE. Specifically, liver function results that exceed two times the upper limit of normal, triglycerides greater than 400 mg/dl, and/or hypotension, with a blood pressure <90mmHg in adults or <the 5th percentile for age in children after taurine supplementation, will

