Pregnancy testing will be done on day 1, one day prior to the administration of taurine and reviewed by 5:00 PM that day. Positive test results will exclude the individual from participation in the study. A physical examination (to include blood pressure) and the Adverse Event Sheet Questionnaire will be completed on day 1 and just prior to taurine administration respectively. They will be repeated after administration of the last taurine dose. This data will be reviewed within 5 working days after the subject has completed the study protocol. Liver function study results that exceed two times the upper limit, triglycerides results that are greater than 400 mg/dl, and/or hypotension (blood pressure <90mmHg in adults or < the 5th percentile for age in children) as well as any clinically significant alteration in safety monitoring laboratory studies (as assessed by the co-investigating MD) that is present in two or more subjects in the setting of normal subject values before taurine supplementation will be reported to the co-investigators, FDA, COMIRB, CTRC, and Safety Officers within 5 working days of knowledge of this data. The protocol will be temporarily suspended pending review of collected data and recommendation about study continuance by Safety Officers, FDA, COMIRB and CTRC.

All unanticipated problems and unanticipated events will also be discussed with one of the co-investigating MDs within five working days of knowledge of the problem or event. Any identified trend in AEs will also be discussed within five working days of knowledge of the trend with one of the co-investigator MDs.

Compiled data will be examined for safety after 2, 4, and 8 subjects have completed the protocol and at the end of the study by the PI, co investigators and data Safety Officers. The PI, co-investigators and the data Safety Officers board will be looking for repeat adverse events (AEs) or trends in AEs.

SAEs will be reported to the study project manager, the PI or one of the lead site co-investigator MDs, FDA, COMIRB, local IRB as per their requirement, and the CTRC within five working days of knowledge of the event. In addition, the data Safety Officers and PI and co-investigators will convene within one week of reporting of a SAE.

C. Describe both subject discontinuation criteria and protocol stopping criteria:

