With respect to the FMD studies, if an adult systolic blood pressure is < 105 mmHg or a child's blood pressure is < 10th percentile for age, nitroglycerin will not be administered. The subject will otherwise be maintained in the study.

With respect to the study in general, subject discontinuation criteria are as follows.

- Positive pregnancy test
- Any SAE that is possibly related to the study protocol.

Protocol stopping criteria are listed below. Such events will result in the study being temporarily suspended pending review of collected data and recommendation about study continuance by Safety Officers, FDA, COMIRB and CTRC.

- Any SAE that is possibly related to the study protocol.
- Liver function study results that exceed two times the upper limit, if triglycerides are greater than 400 mg/dl, and/or if hypotension (blood pressure <90mmHg in adults or < the 5th percentile for age in children) is present in two or more subjects in the setting of normal subject values before taurine supplementation.
- Any clinically significant alteration in safety monitoring laboratory studies, as assessed by the co-investigating MD and/or the Safety Officers that is present in two or more subjects in the setting of normal subject values before taurine supplementation.

Currently there is no funding source outside of the university, thus we do not expect an outside agent to have authority to suspend this trial, other than general regulatory authorities of the institution and the FDA in its general capacity to oversee drugs and food supplements. Actions that result in suspension or termination of the protocol, whether by COMIRB or some other entity, will be reported to the Pediatric General Clinical Research Center and the IRB verbally within 24 hours and via written documentation within 2 working days.

D. Plans for assuring data accuracy and protocol compliance:

The PI will conduct protocol compliance checks. Accuracy of the laboratory data related to safety is assured via use of Clinical Laboratory Improvement Amendments (CLIA) certified laboratory.

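### The SAE reporting flow allows five working days before the PI or a lead-site physician is told, so a suspension may come after a patient dosed at another site has taken all remaining doses

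*Combined protocol and SAP*

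**What the plan says.** - **Report to the lead site.** The monitoring and reporting flow at the end of section 8.B states that "SAEs will be reported to the study project manager, the PI or one of the lead site co-investigator MDs", together with the FDA, COMIRB, "local IRB as per their requirement, and the CTRC within five working days of knowledge of the event". This clause speaks of a lead site and a local IRB, so it is written for several sites. Earlier in 8.B the same limit is given for a co-investigator physician, the Safety Officers and the regulatory bodies.
- **24-hour step.** Section 8.A says "the monitoring PI will discuss the event with one of the co-investigator MDs within 24 hours of knowledge of the event", and gives as its purpose decisions about the data and the safety of all participants.
- **Relatedness.** In section 8.B the PI and a co-investigating physician "will determine the severity of the event and if the SAE or AE is related to the protocol using the categories noted below".
- **Hold on new patients.** Section 8.B: "No new patients will be enrolled or studied until the SAE has been reviewed and appropriate action taken by the above listed bodies". No delay is attached, and no time is set for telling the other sites.
- **Suspension.** Among the stopping criteria in section 8.C is "Any SAE that is possibly related to the study protocol". It leads to temporary suspension pending review, with no time limit stated.
- **Schedule and size.** Section 5.G: "The study will usually start on a Thursday and end on a Tuesday", with taurine twice daily for 4½ days. Section 5.D: "Up to 16 patients will be exposed to taurine and analyzed".

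**The concern.** A single possibly related SAE is meant to stop the study. The people who must make that rating are the PI and a co-investigating physician, and they cannot rate an event they have not heard of. For an SAE first known at a site other than the lead site, the flow in 8.B lets up to five working days pass before the PI or a lead-site physician must know. A taurine course is shorter than that. If another site has a patient in course at that time, the course may be over before the suspension can begin.

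At stake is the further exposure of other patients, including children from age 8. The patient who had the event is covered separately by the discontinuation criterion in 8.C. No endpoint, sample size or error rate is involved.

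**Working it through.** **Inputs.** The course is twice daily for 4½ days (5.G). The visit table in 5.H and the blood-draw table put the first dose on Friday morning after the 8 AM baseline and the end of dosing on Tuesday. The reporting limit is five working days (8.B). Four assumptions are mine: patients are dosed at more than one site in the same period; doses fall at 8 AM and 8 PM; the site learns at noon; and the limit expires at 5 PM on the fifth working day, with the day of knowledge not counted.

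**The plan's own figure.** 4.5 days × 2 = 9 doses. First to last dose takes (9 − 1) × 12 h = 96 h, from Friday 8 AM to Tuesday 8 AM.

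**Length of the limit.** Five working days is 7 calendar days if the site learns Monday to Friday, 6 if Saturday and 5 if Sunday. Each is longer than 96 h.

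**Count.** Dose i falls at Friday 8 AM + 12 h × (i − 1), for i = 1 to 9. Count the doses after the site's knowledge and before the limit. For a patient in course, the doses already taken by noon are 1 on Friday, 3 on Saturday, 5 on Sunday and 7 on Monday. That leaves 9 − 1 = 8, 9 − 3 = 6, 9 − 5 = 4 and 9 − 7 = 2.

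| Site learns | Limit (5 PM) | Patient in course elsewhere | New patient elsewhere, if the hold is not applied |
|---|---|---|---|
| Mon | next Mon | 2 | 7 |
| Tue | next Tue | 0 | 9 |
| Wed | next Wed | 0 | 9 |
| Thu | next Thu | 0 | 9 |
| Fri | next Fri | 8 | 1 |
| Sat | next Fri | 6 | 1 |
| Sun | next Fri | 4 | 1 |

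In every row the patient in course takes all remaining doses before the limit.

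**Sensitivity.** If a working day of knowledge counts as day one, the limit moves to Friday for Monday knowledge and to Thursday for Friday knowledge. The in-course column does not change, because every limit still falls after the Tuesday morning dose. For a new patient, Wednesday and Thursday still allow 9. Tuesday falls to 7, since the limit is then Monday (2 + 2 + 2 + 1). Under the main count, the Tuesday figure of 9 needs the limit to fall after the 8 AM dose that day.

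**With 24 h to notification and 24 h more to the rating.** For a patient in course, the doses possible before a suspension are 4 (Fri), 4 (Sat), 4 (Sun), 2 (Mon) and 0 (Tue to Thu). For example, Friday noon to Sunday noon covers Fri PM, Sat AM, Sat PM and Sun AM. For a new patient, 1 dose is possible before the hold if the site learns on Thursday and 0 otherwise. Over every hour of the week the maxima are 4 in course and 2 new.

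**The case against.** The strongest reply is that the five-day list is for formal reports and that the 24-hour step in 8.A is the working safety mechanism. The text gives this support. A co-investigator physician has both a 24-hour step (8.A) and a five-working-day limit (8.B), so a place on the longer list does not show that first notice may take that long. The purpose stated for the 24-hour step also extends to all participants. This stands as far as it goes. A reader might infer that 8.A and 8.B contradict each other, but a 24-hour duty satisfies a five-day maximum. What remains is ambiguity: the actor in 8.A is the monitoring PI, and nothing visible says that the clock starts when a site learns, or that a site must tell the PI in time to meet it.

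The hold on new patients also stands. It is written without delay, so the new-patient column needs a site that has not been told and therefore does not apply it. That is an inference.

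The flow diagram is not shown, and Supplement VI appears only as a heading. Either may contain a faster limit, so a reader should not conclude that the plan has none.

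Finally, harm needs several things together: an SAE first known away from the PI, possibly related, reported late within the limit, with another patient in course elsewhere. The documents are mixed on where dosing occurs. Section 5.C names three centres, the laboratory footnotes in 5.H give a Colorado-specific entry, and the advertisement leaves the site blank. Yet the consent plan mentions travel to Denver, and 5.G describes the Colorado pharmacy. Overlapping courses are not documented.

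**Conclusion.** The point holds as a limited safety gap that should be fixed. The reporting flow in 8.B permits up to five working days before the PI or a lead-site physician is told, and it is unclear whose knowledge starts the 24-hour clock in 8.A. If patients are dosed at more than one site in the same period, a patient in course elsewhere could take up to 8, 6 or 4 further doses (site learns Friday, Saturday or Sunday) before a suspension under 8.C can be triggered. A new patient elsewhere could take all 9 within the limit (site learns Tuesday to Thursday), only if the hold is not applied there.

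A reader might go further and count Monday as well, giving 9 of 9 doses on four of seven days. That adds a further 24 hours after the five-day limit, which the ambiguous clause in 8.A does not establish. Within the limit itself Monday gives 7.

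All counts are maxima, since a site may report sooner. With at most 16 patients exposed and an SAE described in 8.A as not anticipated, the situation is likely to be rare. It matters only if an SAE occurs, which is when the rule has to work.

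**What to change.** Amend section 8 in three places:

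1. In the 8.B reporting flow, require each site to notify the PI or a lead-site physician of any SAE within 24 hours of the site's knowledge. Keep five working days for the written reports to the other bodies.
2. State that the 8.B hold on new patients starts at all sites on that notification.
3. State that the 8.A discussion and the 8.B relatedness rating follow within 24 hours of that notification, so that a suspension under 8.C can start within 48 hours of site knowledge.

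For a patient in course, this cuts the maximum from 8 to 4 doses (Friday) and from 6 to 4 (Saturday). The Sunday and Monday figures (4 and 2) do not change, because those courses end within 48 hours. For a new patient, the maximum falls from 9 to 2. If the event is rated not related, dosing continues under either text.

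The cost is a short amendment and one call or e-mail per SAE, with no added patients, visits or samples.
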